9.1.1. Inclusion Criteria

Patients must meet all of the following inclusion criteria to be eligible for inclusion in the study:

- 1. Age ≥ 60 years.
- 2. Evidence of pneumonia within first 48 hours of hospital admission based on:
 - a. Documented pneumonia diagnosis or clinical suspicion of pneumonia* at the time of enrollment **OR**;
 - b. Radiologic findings consistent with pneumonia (eg, increased pulmonary density due to infection and/or alveolar infiltrates [multilobar, lobar, or segmental]) **AND** presence of ≥2 of following 10 clinical signs or symptoms:
 - i. fever (oral temperature >38.0°C or tympanic temperature >38.5°C);
 - ii. hypothermia (<35.5°C measured by a healthcare provider) within 24 hours before enrollment;

iii. chills or rigors;

iv. pleuritic chest pain;

- v. new or worsening cough;
- vi. sputum production;
- vii. dyspnea (shortness of breath);

viii. tachypnea (respiratory rate >20/min);

- ix. malaise; or
- x. abnormal auscultatory findings suggestive of pneumonia (rales or evidence of pulmonary consolidation including dullness on percussion, bronchial breath sounds, or egophony).
- 3. Evidence of a personally signed and dated informed consent document indicating that the patient (or a legally acceptable representative) has been informed of all pertinent aspects of the study.

*Note: Pneumonia may be clinically suspected, based on any combination of radiologic and laboratory findings as well as signs, symptoms and other clinical findings, regardless of a formal admission diagnosis or other diagnoses assigned during hospitalization and other acute or chronic comorbidities, including other pulmonary diagnoses.

9.1.2. Exclusion Criteria

Patients meeting any of the following criteria will not be included in the study:

- 4. Any patient who develops signs and symptoms of pneumonia after being hospitalized for ≥48 hours (either at current hospital, another transferring hospital, or a combination of these).
- 5. Previously enrolled subjects readmitted ≤ 14 days after discharge for their study qualifying admission.
- 6. At the time of enrolment, pneumonia has been excluded as the diagnosis or another diagnosis confirmed.

9.1.3. Variables

Please see listing of data collection per visit, Section 10.

9.1.4. Data Sources

In the Madrid Region, the primary and secondary medical care records are formally linked for routine clinical use. The information related to vaccine administration will be extracted from a population-based computerized vaccination registry that belongs to the Regional Health System, namely SISPAL (http://www.sanidadmadrid.org/saludpublica/e-sispal, restricted access). SISPAL vaccination registry provides nominal records (name, sex, date of birth) of every vaccine administered (vaccine, lot, date of administration) in the public or private sector to the entire population living in the Madrid Region and provides access to the information for every health care practitioner working in the public sector after request. The electronic database was created in 2005 but contains information on vaccination prior to 2005, transferred from manual records. Self-reported vaccination history will not be used as it has been demonstrated that vaccine self-reported data could significantly overestimate the vaccine coverage when compared with SISPAL database.²⁸

10. STUDY PROCEDURES

10.1. Surveillance Process

10.1.1. Surveillance Manual

The Surveillance Manual should describe and identify the following:

- Description of the informed consent process, including the staff roles responsible for informed consent.
- Description of the study-level Surveillance Officer role, which will be responsible for coordinating all enrolment activities at the participating sites. Additionally, site-level surveillance coordinators may be utilized.
- Identification of key personnel in each hospital that will assist with enrolment. This list should include the key posts at each ward who will serve as important sources of information for identification of inpatients with pneumonia. Ideally, numerous sub-investigators and site staff across various departments/wards will be involved to ensure constant and complete surveillance.
- Surveillance team structure, training and engagement should be addressed.
- Description of the process for sample collection.
- Establishment of communication and collaboration mechanisms between the surveillance staff and the local laboratory that will manage samples.

- Development of validated links with the testing laboratories for result reporting, if possible.
- Description of the laboratory testing procedures for SP, and methods for safe shipping and handling of the samples.
- A detailed step-by-step description of the screening process. This should include a description of how staff will be contacted to identify patients being admitted with pneumonia. This can also include how hospital admissions records, patient medical records, radiology reports and microbiology reports will be reviewed to identify patients being admitted with pneumonia.
- A step-by-step process of enrolment, including procedures used to identify patients being admitted with pneumonia, consent, enrolment, specimen collection, review of medical records of enrolled individuals, participant follow-up.
- The use of the screening and enrolment log, which will record all identified hospitalised patients admitted with pneumonia, whether or not they are eligible for the study, and whether or not the eligible individuals were enrolled.
- Enrolment will ideally be within 24 hours of admission to the hospital on weekdays but may be enrolled later if admitted on the weekend and/or if person cannot consent during that time period (eg, if intubated). When a potentially eligible patient has been identified for the study (see screening criteria), the pneumonia hospitalisation registry (screening log) will be completed by staff trained to work on the study and then later the patient will be offered participation in the study.

10.2. Screening/Enrolment Log

- The study screening log will be completed by site personnel and be forwarded to the sponsor or its representatives weekly for the required study monitoring and follow-up. The registry will include the following information as permitted by the Independent Ethics Committee (IEC) and may include:
 - Screening date;
 - Hospital site and ward;
 - Sex;
 - Nationality;
 - Surveillance area resident (yes/no);
 - Eligibility if not eligible, why;

- Consented (yes/no);
- Date of consent (day/month/year);
- If declined, reason not consented;
- Study participant ID;
- Date of admission to hospital (day/month/year);
- Year of birth;
- Pneumonia confirmed by Chest radiology (yes/no);
- ICU admission (yes/no);
- Samples collected.

10.3. Visit 1 Day 1 (Screening/Enrolment)

All relevant patients who are eligible via inclusion in the screening process will be offered enrolment to the consented study. The study would be explained by a healthcare professional who will also answer any questions the patient has before taking written informed consent to participate in the study. Once consent has been given, data and samples will be collected per the SCHEDULE OF ACTIVITIES in Section 6.

- If the patient meets all the inclusion criteria and none of the exclusion criteria, they will be informed of this study and asked for written informed consent (see Section 15.1).
- Once informed consent is obtained, a participant number will be assigned to the patient. The participant number will contain no initials or any other personal data that may identify the patient. Hospitalised participants that are recruited more than once as new cases (see Inclusion Criteria, Section 9.1.1) will be assigned a new participant number. Multiple events for a single participant will be linked in the electronic Case Report Form (eCRF) (for example, capturing prior study number(s) in the eCRF for the new event(s)).
- Collect Adverse Events (AEs) and Research Related Injury (RRI) as outlined in Section 16.
- Collection of urine for pneumococcal testing per Section 11.2.3.
- Collection of saliva sample at selected study sites per Section 11.2.4.

Specifically, at this visit the following data will be recorded in the eCRF:

PFIZER CONFIDENTIAL CT45-GSOP-RF152.0 Low-Interventional Study Protocol Template 05-Dec-2019 Page 35 of 70

- Date informed consent is obtained.
- Eligibility of the subject. It will be confirmed that the participant meets all inclusion criteria and no exclusion criteria to be eligible for the study.
- Demographic data: date of birth; sex, nationality, country of birth.
- Surveillance area resident: Do you live in the study catchment area? (yes/no).
- Residence setting (eg, nursing home, long-term care facility for those with disability or dependency, private residence, or other).
- Weekly exposure to children <5 years of age.
- Body Mass Index (BMI) (height and weight).
- Smoking status (current/previous/never).
- Alcohol/drug use.
- Vaccination history.
 - Pneumococcal, last date of administration for PCV13 and PPV23. PCV20 immunisation will also be collected once available in the region.
 - Influenza vaccination in last year, date of administration.
 - COVID-19 vaccination, dates and vaccines types.
 - RSV vaccination, dates and vaccine types.
- Hospitalisation data:
 - Dates and time of admission/discharge for qualifying admission.
 - ICU stay (yes/no).
 - Number of days in ICU.
 - Mechanical ventilatory support (invasive and non-invasive), if used and type.
 - Number of days of mechanical ventilator use.
 - Acute respiratory distress syndrome (ARDS) diagnosis during illness.

PFIZER CONFIDENTIAL CT45-GSOP-RF152.0 Low-Interventional Study Protocol Template 05-Dec-2019 Page 36 of 70

- Readmission within 14 days of discharge (If yes, dates of admission/discharge).
- Symptoms of qualifying pneumonia illness mentioned in inclusion criteria.
- Date of illness onset.
- Vital signs (initial respiratory rate, pulse oximetry, blood pressure, heart rate).
- Level of oxygen supplementation during pulse oximetry measurement (FiO2).
- SOC chest radiography results (eg, CXR and computed tomography [CT] scan), including if consistent with pneumonia per standard outlined in Section 11.3.
- SOC microbiology test results including test and specimen type:
 - Blood cultures.
 - Respiratory microbiology testing, including bacterial (eg, PCR and culture), viral testing (eg, RSV, influenza, and COVID-19), and Gram stain results.
 - All standard –of care COVID-19 testing during the qualifying illness will be recorded with result.
 - Pneumococcal testing (eg, *BinaxNOW*[®] or another pneumococcal antigen urine test).
 - Other body fluid/tissue sterile under normal conditions.
- CAP severity/prognosis scale (Confusion Respiratory Rate Blood Pressure [CRB-65] and Pneumonia Severity Index [PSI]) on presentation to hospital if information available from SOC testing to calculate score:
 - CRB-65 score [Contributing data elements: age, blood pressure, presence of confusion, and respiratory rate].
 - PSI score. Contributing data elements are:
 - Altered mental status.
 - Nursing home residency.
 - pH and partial pressure of arterial O2 (PaO2) from atrial blood or arterialised venous blood OR oxygen saturation level (SpO2) measured by pulse oximetry

PFIZER CONFIDENTIAL CT45-GSOP-RF152.0 Low-Interventional Study Protocol Template 05-Dec-2019 Page 37 of 70

and FiO2 during that assessment.

- Blood urea nitrogen.
- Serum sodium concentration.
- Plasma glucose concentration.
- Hematocrit.
- Presence of pleural effusion.
- Relevant medical history:
 - COPD.
 - Asthma.
 - Congestive Heart Failure.
 - Coronary Artery Disease (CAD).
 - Chronic Kidney Disease.
 - Diabetes (with or without complications).
 - Liver Disease.
 - Immunosuppressant Drug Therapy.
 - Autoimmune Disorders.
 - Immunodeficiency.
 - Human Immunodeficiency Virus (HIV).
 - Acquired Immunodeficiency Syndrome (AIDS).
 - Cancer/Malignancy, Solid Tumor only.
 - Cancer/Malignancy, Hematologic only.
 - Organ Transplantation.
 - Cerebrovascular accident (Stroke).
- Number of previous pneumonia events in year prior to admission. PFIZER CONFIDENTIAL CT45-GSOP-RF152.0 Low-Interventional Study Protocol Template 05-Dec-2019 Page 38 of 70

- Healthcare facility exposure in past 3 months, includes inpatients stays, dialysis centers or long-term care, skilled-nursing, assisted-living, rehabilitation, or other healthcare facilities.
- Antibiotic treatment within 14 days prior to admission.

10.4. Visit 2 Day 30 (Final Diagnosis and Event Outcome)

The participant will be followed-up by telephone at 30 to 45 days after hospital admission. The date of the visit, the patient's final diagnosis and outcome for study-qualifying suspected CAP event will be recorded in the eCRF. If patient returns to study hospital for a standard - of care clinic visit for another reason, the visit may occur in person. RRIs will be collected if encountered during the collection of visit-related information or if the patient is contact by phone.

- The following data will be recorded in the study eCRF:
 - Any additional results from standard –of care pneumococcal and viral respiratory testing, including COVID-19 and RSV, that was not captured during Visit 1.
 - Additional information on hospitalisation data eCRF items not captured during Visit 1.
- Principal investigator (PI) or designee should make an outcome assessment of final diagnosis based on any information available over the hospitalisation of the patient. This may include both study and SOC exams, procedures and tests. This data point can be recorded on Day 30 or sooner if available. Final diagnosis categories will include:
 - CAP-radiologically confirmed;
 - CAP-not radiologically confirmed (eg, clinical CAP);
 - CAP-no chest radiology done; or
 - Other diagnosis (not CAP).
 - Acute Bronchitis.
 - Exacerbation of COPD.
 - Empyema/lung abscess.
 - Other Acute Lower Respiratory Infection. PFIZER CONFIDENTIAL CT45-GSOP-RF152.0 Low-Interventional Study Protocol Template 05-Dec-2019 Page 39 of 70

- Acute pulmonary exacerbation of congestive heart failure.
- Non-infectious process.
- Event disposition at 30 days after admission:
 - Fatal/deceased.
 - Not recovered/not resolved.
 - Recovered/resolved.
 - Recovered/resolved with sequelae.
 - Recovering/resolving.
 - Unknown.
- Vital Status (ie, deceased or living), including date and cause of death if deceased.
- RRIs per Section 16.2 and selected exposures and AEs related to Pfizer products per Section 16.3.

Case Definition for Radiologically Confirmed CAP

Patients in whom the treating physician clinically suspected pneumonia who meet the following 2 criteria will be considered to have radiologically confirmed CAP:

- 1. Has a radiologic finding that is consistent with pneumonia (eg, pleural effusion, increased pulmonary density due to infection, the presence of alveolar infiltrates [multilobar, lobar or segmental] containing air bronchograms); AND
- 2. Illness involves ≥ 2 of the following signs or symptoms:
 - a. fever (oral temperature >38.0°C/100.4°F or tympanic temperature >38.5°C/101.2°F) within 24 hours before enrolment;
 - b. hypothermia (<35.5°C measured by a healthcare provider) within 24 hours of enrolment;
 - c. chills or rigors;
 - d. pleuritic chest pain;
 - e. new or worsening cough;

- f. sputum production;
- g. dyspnea (shortness of breath);
- h. tachypnea (respiratory rate >20/min);
- i. malaise;
- j. abnormal auscultatory findings suggestive of pneumonia (rales or evidence of pulmonary consolidation including dullness on percussion, bronchial breath sounds, or egophony).

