	Population of 60 years and older	Percentage of people of 60 years and older
Hospital Universitario de Móstoles, Móstoles	35,106	25.5%
Hospital Universitario Rey Juan Carlos, Móstoles		
Hospital Universitario Fundación Alcorcón, Alcorcón	46,802	27,1%

Note: Hospital Universitario de Móstoles and Hospital Universitario Rey Juan Carlos have the same geographic catchment area.

Figure 1. Map of Study Locality

PCV13 effectiveness against hospitalised VT-Pneumococcal CAP will be assessed using a TND, which is a modified case-control study. In the TND, researchers are not aware of participants' case/control status at recruitment, but later classify the participants into cases or controls according to the test results. Cases are participants testing positive for PCV13 serotypes by any method, including routine culture from blood, high-quality respiratory culture, or serotype-specific UAD1. For the analysis, PCV13 serotypes will be defined as all serotypes contained in PCV13 (ie, 1, 3, 4, 5, 6A, 6B, 7F, 9V, 14, 18C, 19A, 19F, 23F).

PFIZER CONFIDENTIAL CT45-GSOP-RF152.0 Low-Interventional Study Protocol Template 05-Dec-2019 Page 29 of 70

Controls are hospitalised patients with pneumonia meeting the inclusion and exclusion criteria but testing negative for PCV13-type infection or related serotypes. Vaccine effectiveness is calculated as follows:

 $VE = (1 - vaccination odds ratio) \times 100\%$.

TND validity is predicated on the core assumption that the intervention (vaccine) has no effect on other non-targeted aetiologies resulting in similar illness/disease incidence in the vaccinated and unvaccinated. Compared with conventional case-control or cohort designs, the TND is less susceptible to bias caused by differences in health-care- seeking behaviour among cases and controls and the use of non-specific outcome measurements. However, TND is prone to selection bias, residual confounding due to healthy vaccinee effects and risk-based vaccination strategies, bias due to indirect effects of the vaccine, and misclassification of false-negative cases and controls, these concerns will be addressed, discussed and acknowledged as limitations of the study.

Further, statistical adjustments will be undertaken to control for confounding (eg, propensity score matching).

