12.1.3. Analysis Populations

12.1.3.1. Vaccine Effectiveness CAP Population (Primary Analysis Population)

The Primary Analysis Population will include all participants who:

- 1. Meet all inclusion and exclusion criteria.
- 2. Have a final diagnosis consistent with CAP (CAP-Radiologically Confirmed; CAP-Not Radiologically Confirmed or CAP-no chest radiology done).
- 3. Meet the definition of either case or test-negative control from Section 12.1.1.
- 4. Have \geq 5 combined years of pneumococcal vaccination history available.
- 5. Did not receive any pneumococcal vaccination ≤30 days prior to urine sample collection.
- 6. Have not received PCV20 if available in surveillance region during study.

This population will be analysed overall and restricted to immunocompetent subjects which will be all subjects not noted to the immunocompromised in Table 7.

Table 7.Categorization of Risk Factors by Immunocompetence³

Risk factor	Spain's Categorization		
Age	60 +		
Diabetes mellitus	immunocompetent		
Alcoholism	immunocompetent		
Chronic heart disease	immunocompetent		
Chronic liver disease	immunocompetent		
Chronic lung disease	immunocompetent		
Smoking	immunocompetent		
Congenital or acquired asplenia	immunocompromised		
Cerebrospinal fluid leak	immunocompetent		
Cochlear implant	immunocompetent		
Congenital or acquired immunodeficiencies	immunocompromised		
HIV infection	immunocompromised		
Chronic renal failure	immunocompromised		
Nephrotic syndrome	immunocompromised		
Leukemia	immunocompromised		
Hodgkin's disease	immunocompromised		
Lymphoma	immunocompromised		
Generalize malignancy	immunocompromised		
Iatrogenic immunosuppression	immunocompromised		
Solid organ transplant	immunocompromised		
Multiple myeloma	immunocompromised		
Antineoplastic chemotherapy	not specified		
Occupational risk with exposure to metal fumes	not specified		
Bone marrow transplantation	immunocompromised		
Neurologic diseases (eg, cerebral palsy and seizures)	not specified		
Prior IPD	immunocompetent		

These populations will serve as the primary analysis population for the primary endpoint and the secondary objective of calculating VE for PPV23.

³ Official Regional Immunisation Programme in the Community of Madrid, 2019.

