## Cases and Controls for VE against PCV13

The cases are the patients with CAP (i.e., enrolled population who have a final diagnosis consistent with CAP) and in whom PCV13 serotypes are identified by any method including UADs, routine culture of blood, pleural fluid, or other high-quality respiratory tract specimen. PCV13 serotypes are as follows: 1, 3, 4, 5, 6A, 6B, 7F, 9V, 14, 18C, 19A,

DMB02-GSOP-RF02 5.0 Statistical Analysis Plan Template 05-Dec-2019 PFIZER CONFIDENTIAL Page 9 TMF Doc ID: 98.03 19F and 23F. Only sputum isolates from high-quality specimens (Appendix 4) will be considered in assigning case status. Participants with VT serotype who also have a Non-Vaccine Type (NVT) serotype will also be classified as cases.

The following criteria must be met to be a control:

- hospitalized patient with CAP
- met the inclusion/exclusion criteria, and
- PCV13 or related serotype (e.g., 6C) are not identified from any sources

A second model will be developed excluding immunocompromised persons (Appendix 2.4) to evaluate PCV13 VE without those who may not be able to respond to the vaccine.

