#### 4.5. The CAP Population

The CAP population will include the per-protocol population and who have a final diagnosis consistent with CAP (CAP-radiologically confirmed; CAP not radiologically confirmed, or CAP-no chest radiology done).

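### Entry to the VE population turns on a site-assigned final CAP diagnosis that may use pneumococcal test results, so PCV13 effectiveness may be modestly biased

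*Protocol*

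**What the plan says.** The Primary Analysis Population in Protocol 12.1.3.1 requires that participants "Have a final diagnosis consistent with CAP". The SAP repeats the condition in its case definition (3.1, "enrolled population who have a final diagnosis consistent with CAP") and in the CAP population (4.5, "who have a final diagnosis consistent with CAP"). CAP without radiological confirmation, or with no imaging at all, also counts.

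Protocol 10.4 has the principal investigator or a designee assign the "final diagnosis based on any information available over the hospitalisation of the patient". On sources it adds: "This may include both study and SOC exams, procedures and tests". On timing: "This data point can be recorded on Day 30 or sooner if available". The alternatives to CAP include acute bronchitis, COPD exacerbation and acute exacerbation of heart failure.

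By then the site already holds the vaccination record, because the Visit 1 eCRF in Protocol 10.3 includes "Pneumococcal, last date of administration for PCV13 and PPV23". SOC culture and urine antigen results are also recorded at Visit 1 and completed at Visit 2.

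The only statement on masking is in Protocol 9.1, where "researchers are not aware of participants' case/control status at recruitment, but later classify the participants into cases or controls". It covers recruitment and not the final diagnosis. No adjudication is planned.

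**The concern.** A test-negative design compares people who passed the same gate before their result was known. Here there are two gates. The first, clinical suspicion at enrolment, comes before the result. The second, the final diagnosis, may come after some of the results. A doubtful patient with a positive pneumococcal test is easier to call CAP than the same patient with a negative one, who may be relabelled as a COPD or heart failure exacerbation and leave the control group.

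That matters because Protocol 3 and 7 name COPD and heart failure as reasons to give PCV13, and Protocol 3 expects vaccinated people to be enriched for risk conditions. Dropping such patients only when they test negative would lower coverage in controls but not in cases, and so lower the estimated VE.

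**Working it through.** **Inputs from the plan.** Protocol Table 6 (scenario 2) and SAP 2.2: coverage in controls 15%, VE 60% (OR 0.40), 170 cases, 1,692 controls, two-sided alpha 0.025, 80% power. Coverage in cases is 0.40 × 0.15 / (1 − 0.60 × 0.15) = 0.0659. The Fleiss formula with continuity correction then gives 170 cases, as stated. Nothing below changes that number.

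**When does selection bias the OR?** Let s be the probability of being kept as CAP:

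observed OR = true OR × (s[case, vaccinated] × s[control, unvaccinated]) / (s[case, unvaccinated] × s[control, vaccinated])

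The retention rates here are assumptions:
- Cases 100%, controls 80% or 70% whatever their vaccination: VE 60.0%.
- Vaccinated 75%, unvaccinated 80%, in cases and controls alike: VE 60.0%.
- All cases kept, controls kept 75% (vaccinated) against 80% (unvaccinated): 0.40 × 0.80/0.75 = 0.427, VE 57.3%. With 70% against 80%: 0.457, VE 54.3%.
- The reverse, 80% (vaccinated) against 75% or 70% (unvaccinated): VE 62.5% or 65.0%.
- Vaccinated cases kept at 95% or 90%, everyone else kept: VE 62.0% or 64.0%.

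So retention must depend jointly on test result and vaccination. Either alone leaves the OR unchanged.

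**Size through the COPD and heart failure route.** Assume a share d of enrolled patients is doubtful, with coverage c in doubtful controls and 13% in other controls. The OR is 0.40 in each group, all test-positive doubtful patients are kept, and a fraction k of test-negative ones is kept. With g(p) = 0.40p / (1 − 0.60p):

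- coverage in cases = d·g(c) + (1 − d)·g(0.13)
- coverage in controls = [d·k·c + (1 − d)·0.13] / [d·k + 1 − d]

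| d, c | Cases | Controls at k = 0.5 | VE, k = 1 | VE, k = 0.75 | VE, k = 0.5 |
|---|---|---|---|---|---|
| 0.10, 22% | 6.09% | 13.47% | 59.8% | 59.1% | 58.4% |
| 0.20, 28% | 7.20% | 14.67% | 59.2% | 57.2% | 54.8% |

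Overall control coverage at k = 1 is 13.9% and 16.0%, either side of the planned 15%. Against the true 60%, the crude shortfall with selection (k below 1) is about 1 to 5 points.

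**Same model, SOC results only.** Suppose SOC antigen or culture is positive in 50–90% of vaccine-type cases and 5–15% of controls. Doubtful SOC-positive patients are all kept, and SOC-negative ones are kept at rate r of 50–75%. Doubtful cases are then kept at SOC share + (1 − SOC share)·r, and doubtful controls likewise with their own share. Crude VE falls by 0.2 to 3.7 points from the k = 1 values (lowest 55.5%, from 59.2%).

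**After adjustment.** Stratifying exactly on doubtful status returns 60.0% at every k, because retention no longer varies with vaccination within a stratum. With risk level as an imperfect proxy (assumed: 60% of patients at risk, the doubtful patients nested among them with higher coverage), VE is 57.8–59.2%.

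**Scale.** At 170 cases and 1,692 controls the expected cells are 11.2, 158.8, 253.8 and 1,438.2. The SE of log OR is 0.316, and the crude 95% CI for VE is about 26% to 78%.

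**The case against.** A reader might infer four stronger things. The documents do not support them.

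- **That VE is biased because cases and controls are kept by different standards.** That difference alone leaves VE at 60.0%. The documents make a joint dependence plausible but do not establish it.
- **That the crude shortfall is the error in the reported result.** Protocol 12.4.1 treats only adjusted estimates as final. SAP 6.1.1.1 lists risk level, severity score, prior antibiotics and recent pneumonia as candidate covariates. This largely stands. Two limits remain: the at-risk class also pools COPD and heart failure with smoking, treated diabetes and others, and a covariate enters only if it passes a bivariate screen.
- **That UAD results drive the diagnosis.** Protocol 11.2.2 has study urine frozen and shipped in bulk, and Protocol 12.5 implies a lag of about a quarter. Isolates go for serotyping every one to two months. Vaccine-type status will seldom be known at Day 30. SOC urine antigen will be, but it does not separate vaccine types from others, and patients with only non-vaccine types are controls. This dilutes the effect without removing it.
- **That no planned analysis bears on it.** The Broome analysis uses pneumococcus-positive patients on both sides, so favouring positives largely cancels. The radiologically confirmed analysis rests on imaging and signs. Both are partial. Broome answers with a different control group. The radiological analysis still uses the site's final diagnosis and is conditional in the SAP. SAP 6.5.3 tabulates vaccination by CAP versus non-CAP, but not by test result.

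It is also fair that Protocol 9.1 already names selection bias as a concern to be addressed, and that exclusion criterion 6 shrinks the doubtful pool. Neither deals with this gate.

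**Conclusion.** The point holds as a modest, correctable weakness. The plan expressly allows pneumococcal results to inform who stays in the VE population, and no planned VE analysis ignores the final diagnosis. VE may be biased. Through the COPD and heart failure route the likely direction is downward: roughly 1 to 5 points crude with 10–20% doubtful patients, coverage of 22–28% in them, and a quarter to a half of the test-negative ones dropped. The shortfall is about 1 to 2 points under the one imperfect-adjustment scenario examined, and nil if the diagnosis ignores test results. Knowledge of vaccination could move it either way. None of these retention rates comes from the documents.

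A larger effect can be constructed. If every non-CAP patient were dropped when negative and kept when vaccine-type positive, with no vaccine effect in them, VE could fall as low as 45.5% (20% non-CAP, 3% of them positive, 35% coverage). Nothing in the plan supports so strict a rule, so I do not rest the point on it. Any likely bias is small beside the sampling error. The reason to act is that acting costs little.

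**What to change.** 1. **Protocol 10.4.** State that the final diagnosis is assigned without the study UAD, central BinaxNOW or saliva results, and is locked before those results are released to the site. Given the bulk testing of urine, this should cost only wording. It concerns a study classification and changes no care. SOC results cannot be withheld and remain in use.
2. **SAP 6.1.1.2.** Add one sensitivity VE in all per-protocol participants with a valid serotype test regardless of final diagnosis, otherwise with the primary VE exclusions and covariates. Tabulate final diagnosis by vaccine-type result and PCV13 status. This uses data already collected, covers the SOC route that the first change leaves open, and costs one model and one table.

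The added analysis will admit some patients without CAP, including possible false cases. It is a check on selection and does not replace the primary estimate. I do not propose masking the assessor to vaccination: site staff complete the Visit 1 eCRF, so that could need a separate assessor. The sample size is unchanged.
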